## 1.0 OBJECTIVES / SPECIFIC AIMS

The objective of this study is to establish the safety, feasibility, tolerability, and acceptability of high-dose accelerated intermittent theta burst (iTBS) repetitive transcranial magnetic stimulation (rTMS) to the left dorsolateral prefrontal cortex (dlPFC) in patients with amnestic Mild Cognitive Impairment (aMCI). We also seek to obtain preliminary efficacy data as well as feasibility / acceptability data of computerized cognitive training as an adjunct to iTBS rTMS. The long-term goal of this project is to obtain preliminary data to support future empirical studies of iTBS rTMS for aMCI, including future randomized controlled trials to devise the optimum rTMS therapeutic delivery (with variations in dosing parameters, cortical targeting, and MCI syndrome indications), with the ultimate goal of dementia prevention. *The scientific merit of this pilot study has been peer-reviewed and subsequently recommended for funding through the National Center of Neuromodulation for Rehabilitation (NC NM4R).*

**AIM 1: Establish the safety of an accelerated rTMS protocol for neurocognitive rehabilitation in aMCI.** We hypothesize that accelerated rTMS will be safe as indexed by 1) no clinically significant structural brain changes; 2) no decrements in neurocognitive function; 3) no significant adverse events.

**AIM 2: Establish the feasibility, tolerability, and acceptability of an accelerated rTMS protocol for neurocognitive rehabilitation in aMCI.** We hypothesize that 1) aMCI patients will consider the treatment acceptable and that 2) recruitment and retention will be feasible (> 80% retention).

**EXPLORATORY AIM: Establish the preliminary efficacy of an accelerated rTMS protocol for neurocognitive rehabilitation in aMCI.** We hypothesize that aMCI patients will demonstrate modest improvements on neurocognitive testing and self-reported affective symptoms and quality of life from pre- to post-treatment.

**EXPLORATORY AIM: Establish the feasibility, acceptability of computerized cognitive training as an adjunct to accelerated rTMS in MCI.** We hypothesize that aMCI patients will complete a range of exercises between sessions and at home (feasibility) and will rate the intervention as productive (acceptability).

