## **4.0 STUDY ENDPOINTS**

### **AIM 1: Establish the safety of an accelerated rTMS protocol for neurocognitive rehabilitation in aMCI.**

Primary Outcomes: Clinically significant structural brain changes; Neurocognitive performance changes; Adverse events

Secondary Outcomes: Psychopathology symptom changes

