	Credibility/Expectancy Questionnaire (Post-treatment)* TMS Experience Questionnaire* BrainHQ Experience Questionnaire* Review of systems adverse events questionnaire (Yaejee et al., 2015)		
7	Post-treatment MRI Scans FLAIR, diffusion, T2*/gradient, volumetric scans, resting-state fMRI	Center for Biomedical Imaging	1 - 2 hours
8	1 – 3 weeks post-treatment completion Review of systems adverse events questionnaire (Yaejee et al., 2015) PROMIS Measures: Anxiety, Depression, Applied Cognitive Abilities, Social Participation, General Life Satisfaction, and Fatigue*  BrainHQ exercises	REDCap  Online	10 – 20 minutes  >20 minutes per day
9	4 weeks post-treatment completion PROMIS Measures: Anxiety, Depression, Applied Cognitive Abilities, Social Participation, General Life Satisfaction, and Fatigue* Montreal Cognitive Assessment (MoCA)* TMS Experience Questionnaire* BrainHQ Experience Questionnaire*	REDCap  Video Conference	30 min – 1 hour

\*Option to complete remotely, such as due to COVID-19 precautions. Components of sessions 1&2 and 6&7 may be combined..

**Session 1: In-person Pre-treatment Neurocognitive/Neuropsychiatric Assessment (2 - 3 hours).** Participants will complete computerized cognitive tests from the NIH Toolbox (30-40 minutes). Each of these tests has been extensively normed, compared to traditional neuropsychological measures. Tests from different batteries will be utilized in this study for optimizing a comprehensive but efficient, reliable, and minimally burdensome subset of tests for MCI patients.

For further sample characterization with more traditional and more extensively normed neuropsychological measures, participants will complete the Montreal Cognitive Assessment (MoCA) and the 30-minute battery recommended by the National Institute of Neurological Disorders and Stroke-Canadian Stroke Network (NINDS-CSN) Vascular Cognitive Impairment Harmonization Standards: Semantic and phonemic fluency, Digit Symbol-Coding, Digit Span, Trail Making Test A & B, and Hopkins Verbal Learning Test-Revised. Full scale IQ will be assessed with the Vocabulary and Matrix Reasoning subtests of the WASI-II.

During this session, the Lawton Instrumental Activities of Daily Living Scale (IADL) will be administered in order to verify the participants' functional independence per MCI criteria.

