**Sessions 3-5: rTMS (2 – 3 hours).** A MagVenture MagPro TMS System will be utilized. All participants will receive open-label treatment for approximately eight, 3-minute sessions of intermittent theta burst rTMS on each of three days within an eight-day span. A single session=600 pulses at 120% rMT, iTBS triplets at 50 Hz for 2 s and repeated every 10 s for a total of 190 s to left dlPFC. Total pulses=14,400. To enable adherence and retention, the days do not need to be contiguous. Same day sessions will be separated by 10-15 minutes, but more accounting for participant comfort. After each day of treatment, participants will be asked to complete an rTMS acceptability questionnaire. During treatment breaks participants will complete Momentary Assessment of TMS and 10-15 minutes of Brain HQ exercises between each session and will also have the option of completing tasks at home on intervening days during the treatment schedule. At the end of the final treatment session, participants will be asked to rate the exercises based on difficulty and enjoyment.

**Session 6: In-person Post-treatment Neurocognitive/Neuropsychiatric Assessment (2 - 3 hours).** Within one week following treatment, participants will repeat the pre-treatment neuropsychiatric and neurocognitive assessment for assessment of pre/post treatment changes.

**Session 7: Post-treatment MRI Scans (1 - 2 hours).** Within one week following treatment, participants will repeat the pre-treatment MRI scans for assessment of pre/post treatment changes.

**Session 8: 1 – 3 weeks post-treatment completion.** During the intervening weeks after Sessions 6/7 and before Session 9, the participants will be asked to remotely complete surveys using REDCap. Participants will also be provided with a research account for BrainHQ and asked to engage in at least 20 minutes of brain exercises daily until Session 9.

**Session 9: 4 weeks post-treatment completion.** Participants will again be asked to complete surveys using REDCap. Participants will also be asked to complete the MoCA remotely, as well as acceptability/satisfaction questionnaires regarding the rTMS and BrainHQ interventions.

**Participant Compensation.** Participants will be compensated as follows:

Consent & Session 1:	\$40 for screening and pre-treatment assessments
Session 2:	\$50 for the pre-treatment MRI
Sessions 3 to 5:	\$120 for rTMS treatment (i.e. \$40/day)
Sessions 6 and 7:	\$100 for post-treatment assessments and MRI

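### The cognitive battery is repeated within weeks in a single arm with no alternate forms specified, so practice gains could hide the decrement Aim 1 looks for and inflate the efficacy estimate

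*Combined protocol and SAP*

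**What the plan says.** Section 1.0 makes "no decrements in neurocognitive function" one of three markers of safety under Aim 1. Section 4.0 lists the Aim 1 primary outcomes as "Clinically significant structural brain changes; Neurocognitive performance changes; Adverse events". Neurocognitive change is also the primary outcome of the exploratory efficacy aim.

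The schedule table in section 10.0 lists the NIH Toolbox, the MoCA and the 30-minute NINDS-CSN battery (fluency, coding, Digit Span, Hopkins list learning, Trail Making) at both Session 1 and Session 6. Treatment is given "on each of three days within an eight-day span". At Session 6, no more than a week after treatment ends, "participants will repeat the pre-treatment neuropsychiatric and neurocognitive assessment for assessment of pre/post treatment changes". At Session 9, 4 weeks after treatment, "Participants will also be asked to complete the MoCA remotely".

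The protocol does not mention alternate forms, counterbalancing, correction for practice or a required test order. Section 2.0 states that there is no sham control. Section 12.0 analyses cognition by repeated-measures mixed models under Exploratory Aim 3. Its Aim 1 paragraph covers only MRI review and adverse events.

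On visit length, the table gives 3 to 3.5 hours for Session 1 and 2 to 3 hours for Session 6. The text headings give the same length for both: "In-person Pre-treatment Neurocognitive/Neuropsychiatric Assessment (2 - 3 hours" and "In-person Post-treatment Neurocognitive/Neuropsychiatric Assessment (2 - 3 hours".

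**The concern.** A person who meets the same word list, letters or MoCA items twice within a few weeks may score higher the second time for that reason alone. With one arm, the pre-post difference is treatment effect plus practice, and no model fitted to these data can split the two.

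For Aim 1 the error runs in the unsafe direction: a real decline can be offset and read as no decrement. For the efficacy aim it runs in the flattering direction: practice can pass for the modest improvement that section 1.0 predicts. It would also carry over into the effect sizes that section 12.0 wants for planning later randomised trials. Because analysis cannot remove the artefact, it has to be limited when the tests are given.

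**Working it through.** **Figures in the protocol.** There is no power, margin, SD, correlation or alpha for cognition to reproduce. The only sample-size figures are 40 enrolled and 30 completers (section 6.0). These imply attrition of 1 − 30/40 = 25%. I use n = 30.

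**Retest interval.** From first treatment day to Session 6 is at most about 8 + 7 = 15 days, plus a gap from Session 1 to first treatment that is not stated. Retest within weeks is therefore likely but not capped.

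**Assumptions (none from the documents).** Practice gain g of 0 to 0.4 baseline SD; pre-post correlation r of 0.7, range 0.6 to 0.8; equal variances; two-sided alpha 0.05; paired t-test. With two time points and complete data, a random-intercept mixed model normally gives the same test of time.

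**Step 1: precision.** SD of change = √(2(1 − r)) = √0.6 = 0.775 SD. SE = 0.775/√30 = 0.141 SD.

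**Step 2: practice alone, no treatment effect.** t ≈ g/SE:
- g = 0.2: 0.2/0.141 = 1.41
- g = 0.3: 0.3/0.141 = 2.12 (29 df, p about 0.04)
- g = 0.4: 0.4/0.141 = 2.83

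At r = 0.6 (SE 0.894/√30 = 0.163) the range is 1.22 to 2.45. At r = 0.8 (SE 0.632/√30 = 0.115) it is 1.73 to 3.46.

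**Step 3: masking of a true decline d.** The expected change is g − d. Power is the probability that a noncentral t with 29 df and noncentrality (g − d)/SE falls below the lower 2.5% critical value. For d = 0.5 SD:

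| Practice gain | r = 0.6 | r = 0.7 | r = 0.8 |
|---|---|---|---|
| 0 | 84% | 93% | 99% |
| 0.1 SD | 66% | 78% | 92% |
| 0.2 SD | 43% | 54% | 71% |
| 0.3 SD | 22% | 28% | 39% |
| 0.4 SD | 9% | 10% | 13% |

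For d = 0.3 SD at r = 0.7, power is 54% with no gain, 10% with a 0.2 SD gain and 2.5% with a 0.3 SD gain. In the last case gain and decline cancel exactly.

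**Step 4: session length.** By the table, the range midpoints are 3.25 and 2.5 hours, so baseline is 0.75 hours longer. By the text, they are 2.5 and 2.5 hours, a difference of zero. The two sources conflict, so no fatigue difference can be computed.

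**The case against.** **Silence is not a choice.** Repeating an assessment does not by itself mean reusing the same word list, and form selection may sit in test manuals or visit scripts. This is fair. The claim is only that alternate forms are not specified. For a primary safety outcome, that is still worth a sentence in the protocol.

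**The size is assumed.** This stands. Participants must have impaired memory scores to enter, so gains on list learning may lie below the range used. At 0.1 SD the effect is modest: t of about 0.7, and power of 78% against 93%.

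**Some of these tests may not be the outcome.** Section 2.0 describes the pre/post testing as computerised, and section 10.0 introduces the MoCA and the 30-minute battery for characterising the sample. But the table schedules both again at Session 6, and the text says the repeat is there to assess change.

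**The limitation is acknowledged.** Section 12.0 concedes that results are less compelling without sham. That accepts the missing control; it does not deal with avoidable re-exposure to the same items.

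**A stronger reading about fatigue.** A reader might infer from the table that a longer, more tiring baseline also pushes change upward. The documents do not support this:
- The text gives equal lengths for the two sessions.
- WASI-II is listed last among the cognitive tests and may be done remotely, as may consent and the safety screen.
- The text already places the psychiatric interview after cognition and offers breaks at all in-person sessions.
- Session 6 adds questionnaires of its own.
- Combining an assessment with its MRI visit is allowed at either time point, so any effect could go either way.

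There is therefore no basis here for restricting combined MRI visits or for moving the motor-threshold test.

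**Conclusion.** The point holds for practice. The same instruments are given twice in a single arm at a short interval, the MoCA three times, with nothing specified to limit item-specific practice. Any gain is fully confounded with treatment on an outcome that serves both Aim 1 safety and exploratory efficacy.

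Under the assumed inputs, a gain of 0.2 SD is not significant by itself but cuts power to show a 0.5 SD decline from 93% to 54%. A gain of 0.3 SD can look like improvement and cuts that power to 28%. These figures show what is at stake; they do not predict this trial's result. A decline is fully hidden on average only if the gain is at least as large.

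Fatigue remains a possible further bias of unknown direction. The table and text on session length must be reconciled.

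**What to change.** In section 10.0:

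- Specify alternate equivalent forms of the list-learning test (Sessions 1 and 6) and of the MoCA (Sessions 1, 6 and 9). Do the same for fluency and Trail Making where the instrument provides them. The documents do not say which instruments do, so check this against the manuals.
- Counterbalance form order across participants: two orders for tests given twice, and three Latin-square orders for the MoCA.
- Give the cognitive tests in the same fixed order at Sessions 1 and 6.
- Reconcile the Session 1 duration between the table and the text.

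In the report, state that residual practice remains inseparable from treatment. This covers general test familiarity and any test without alternate forms. State the same for the BrainHQ training that takes place before retest. Alternate forms reduce item-specific practice only.

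The cost is protocol and visit-script wording, extra form sheets and an allocation list for form order. Small differences in difficulty between forms average out in the mean under counterbalancing, but they add some noise to each individual's change score. No participants, visits or arms are added.

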## 10.0 STUDY DESIGN AND METHODS

A summary and timeline of all procedures are outlined and described below.

Session Number	Task Description	Location	Approximate Time Commitment
0	Screening Epic and/or medical record review Keel TMS Safety Screen	Telephone	30 minutes
1	Pre-treatment Neurocognitive/Neuropsychiatric Assessment 
Consent/Safety Consent* Keel TMS Safety Screen* TMS Motor Threshold Test Credibility/Expectancy Questionnaire (Pre-treatment)
 
Cognition Montreal Cognitive Assessment (MoCA) NIH Cognition Toolbox NINDS-CSN 30-Minute Neuropsychological Protocol (Hachinski et al., 2006, which includes Semantic and phonemic fluency, Digit Symbol-Coding, Digit Span, Hopkins Verbal Learning Test-Revised, Trail Making Test) WASI-II (Vocabulary, Matrix Reasoning)*
 
Affective Function/Quality of Life Lawton Instrumental Activities of Daily Living Scale (IADL)* Mini-International Neuropsychiatric Interview (M.I.N.I.)* Columbia Suicide Severity Rating Scale (CSSRS) Geriatric Depression Scale (GDS)* Hamilton Depression Rating Scale (HAM-D)* Young Mania Rating Scale (YMRS)* PROMIS Measures: Anxiety, Depression, Applied Cognitive Abilities, Social Participation, General Life Satisfaction, and Fatigue*
	Center for Biomedical Imaging	3 – 3.5 hours
2	Pre-treatment MRI Scans FLAIR, diffusion, T2*/gradient, volumetric scans, resting-state fMRI	Center for Biomedical Imaging	1 – 2 hours
3-5	rTMS Treatment Sessions Review of systems adverse events questionnaire (Yaejee et al., 2015) Momentary Assessment of TMS 8, 3 min sessions rTMS, interspersed with BrainHQ exercises	Center for Biomedical Imaging	2 – 3 hours per day, for 3 days within a 8-day span
6	Post-treatment Neurocognitive/Neuropsychiatric Assessment 
Cognition NIH Cognition Toolbox Montreal Cognitive Assessment (MoCA) NINDS-CSN 30-Minute Neuropsychological Protocol (Hachinski et al., 2006)
 
Affective Function/Quality of Life Lawton Instrumental Activities of Daily Living Scale (IADL)* Mini-International Neuropsychiatric Interview (M.I.N.I.)* Columbia Suicide Severity Rating Scale (CSSRS) Geriatric Depression Scale (GDS)* Hamilton Depression Rating Scale (HAM-D)* Young Mania Rating Scale (YMRS)* PROMIS Measures: Anxiety, Depression, Applied Cognitive Abilities, Social Participation, General Life Satisfaction, and Fatigue*
	Center for Biomedical Imaging	2 - 3 hours

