To assess neuropsychiatric symptoms and conditions often concomitant with aMCI, participants will then complete the Mini-International Neuropsychiatric Interview (M.I.N.I). The Columbia Suicide Severity Rating Scale (CSSRS) will be administered in order to assess suicide risk. The Geriatric Depression Scale (GDS) Hamilton Depression Rating Scale (HAM-D), and Young Mania Rating Scale (YMRS) will be administered. The computer adaptive test versions of the Anxiety, Depression, Applied Cognitive Abilities, Social Participation and Fatigue PROMIS Measures will also be administered. The PROMIS measures have been selected, specifically for the low-burden nature of the computerized adaptive form and the extensive normative data. Neuropsychiatric conditions other than psychotic disorders and substance use disorders will not

result in exclusion. The Edinburgh Handedness Inventory will be administered to assess hand preference on several forms of manual activity.

The option to remotely complete the M.I.N.I, MoCA, WASI-II, Demographics, Keel TMS Safety Screen, IADL questionnaire, GDS, HAM-D, YMRS, and the PROMIS measures will be given to participants if they are unable to physically come to the Center for Biomedical Imaging for the time being, such as due to COVID19 precautions. Phone calls or video conferencing through musc.doxy.me will be utilized in order to administer and oversee the completion of these assessments.

Comfort and reliability considerations: During the administration of some of the neuropsychological assessments, the participants' verbal responses will be audio recorded for quality control purposes. During all in-person sessions, snacks and water will be offered between testing administrations in order to improve energy, limit fatigue, and promote comfort. Furthermore, multiple breaks will be offered. Finally, participants will be given the option to schedule sessions on the same day, with a break, if additional visits/travel would be burdensome.

**Session 2: MRI Scanning (1 - 2 hours).** At pre- and post-treatment participants will complete FLAIR, diffusion, T2\*/gradient, perfusion and volumetric scans for assessment of structural changes. Participants will also complete a resting-state fMRI scan.

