## 11.0 SPECIMEN COLLECTION AND BANKING (Not Applicable)

## 12.0 DATA MANAGEMENT

### *Analysis*

Aim 1. FLAIR, diffusion, T2\*/gradient, perfusion and volumetric scans will be reviewed by [name] for any new signal abnormality. Adverse events will be surveyed and summarized.

Aim 2. Retention (i.e., defined as completion of all study sessions) will be determined. Participants will also complete a survey regarding acceptability, including qualitative responses for treatment modification.

Exploratory Aim 3. Neurocognitive performance and affective symptoms/quality of life will be analyzed with repeated-measures mixed models.

Exploratory Aim 4. BrainHQ usage/retention, performance, and acceptability will be analyzed with repeated-measures mixed models.

**Power Considerations.** The aims of this study are to determine safety and feasibility. The retention rate of 80% was determined to ensure that recruitment in the planned follow-up studies would be feasible in the longer time span allowed by future grants. Although these results will not be as compelling in the absence of a sham control, these data will give us an estimate of the

potential effect sizes and response variability that we can anticipate in future randomized controlled trials.

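### The 4-week MoCA is planned as remote while the earlier MoCAs are in person by default, so 4-week MoCA change is largely confounded with test mode

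*Combined protocol and SAP*

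**What the plan says.** All of the scheduling is in Section 10.0.

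- **Session 9 (4 weeks).** The text states "Participants will also be asked to complete the MoCA remotely". The table entry reads "Montreal Cognitive Assessment (MoCA)* TMS Experience Questionnaire", and the location column lists REDCap and video conference. The asterisk is defined as "Option to complete remotely, such as due to COVID-19 precautions". The NIH Toolbox and the NINDS-CSN battery are not repeated at this visit. The PROMIS Applied Cognitive Abilities measure is, but it is self-report.
- **Sessions 1 and 6.** Both are headed as in-person assessments. The Session 1 table entry, "Montreal Cognitive Assessment (MoCA) NIH Cognition Toolbox", has no asterisk on the MoCA, and neither does the Session 6 entry.
- **Exception at Session 1.** The Session 1 text says "The option to remotely complete the M.I.N.I, MoCA, WASI-II" and further instruments will be offered to participants who are unable to come to the imaging center, by phone or video. The missing asterisk in the table contradicts this.
- **Analysis (Section 12.0, Exploratory Aim 3).** "Neurocognitive performance and affective symptoms/quality of life will be analyzed with repeated-measures mixed models". No time points, contrasts or mode term are given, and there is no instruction to record mode.
- **Design (Sections 2.0 and 3.0).** Open label, with no sham group.

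**The concern.** A participant on the default schedule takes the MoCA in person twice and then remotely at the final visit. If remote administration shifts scores in either direction, the shift enters the 4-week change in full. No concurrent group tested on the same schedule exists to subtract it out.

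The 4-week MoCA is the only standardized test score collected after the first post-treatment week. A repeated-measures model of cognitive performance would naturally include it, and the plan does not exclude it. A mode artefact could then be read as a durable gain or as late decline, and could be carried into the effect-size estimates that Section 12.0 wants for future randomized trials.

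**Working it through.** The plan gives no alpha, SD, effect size or power calculation for the MoCA, so there is no figure to reproduce. The check is whether mode can be separated from time, followed by an illustration of the consequence.

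**Inputs from the documents.** 30 target completers (Section 6.0); MoCA at Sessions 1, 6 and 9 (Section 10.0); single arm.

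**Inputs that are assumptions.** Mode has one additive effect of δ points; phone and video are equivalent; all Session 9 MoCAs are remote and all Session 6 MoCAs in person; a share f of baselines is remote; the SD of individual change is 2, 2.5 or 3 points.

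**1. Identifiability.** Take a model with an intercept, a Session 6 effect, a Session 9 effect and a mode effect (four columns).
- No remote baselines: the mode column equals the Session 9 column. The rank is 3 of 4, so the two effects cannot be separated and no covariate can change that.
- 6 of 30 baselines remote: the rank is 4 of 4, so they can be separated in principle.

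**2. Price of the adjustment.** With participant effects in the model, adding a mode term multiplies the standard error of the Session 9 effect by √(1 + 0.75(1−f)/f).

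| Remote baselines | f | SE multiplier |
|---|---|---|
| 0 of 30 | 0 | not identified |
| 3 of 30 | 0.10 | √7.75 = 2.78 |
| 6 of 30 | 0.20 | √4 = 2.00 |
| 15 of 30 | 0.50 | √1.75 = 1.32 |

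These shares are illustrative; the documents give none.

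**3. Bias without a mode term.** Expected 4-week change = true change + (1−f)δ. Per 1-point shift the bias is 1.00 point at f = 0, 0.75 at f = 0.25 and 0.50 at f = 0.50.

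**4. Chance that mode alone reaches nominal two-sided p<0.05.** Paired t-test, n = 30, 29 degrees of freedom, f = 0, no true change. The noncentrality is δ√30/SD. For δ = 1 and SD = 2.5 the standard error is 2.5/√30 = 0.456, the noncentrality is 1/0.456 = 2.19, and the rejection probability is 56%.

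| Mode shift δ | SD 2 | SD 2.5 | SD 3 |
|---|---|---|---|
| 0 | 5% | 5% | 5% |
| 0.5 | 26% | 19% | 14% |
| 1 | 75% | 56% | 42% |
| 1.5 | 98% | 89% | 75% |
| 2 | 100% | 99% | 94% |

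Remote baselines (f > 0) would lower these figures, because the bias shrinks by the factor 1−f.

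**The case against.** **Complete confounding is not established.** A reader might infer that mode and time are fully aliased and that a mode effect can never be estimated. The documents do not support that: the Session 1 text permits remote baselines, and even a few make the mode effect estimable. This part of the objection stands. The rescue is weak, though. With 3 to 6 remote baselines out of 30, the adjusted standard error is 2.78 to 2.00 times larger, remote testing is tied to who could not attend, and phone may be mixed with video.

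**The plan names no baseline-to-week-4 comparison.** The exploratory hypothesis in Section 1.0 concerns change from before to after treatment, and Section 10.0 assigns that comparison to Session 6. This also stands: the 4-week contrast is inferred from a one-sentence analysis plan that neither includes nor excludes it.

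**The safety reading does not depend on Session 9.** A reader might infer that the hypothesis of no cognitive decrement rests on the remote MoCA. It does not. Section 15.0 places that check in the batteries given before and after treatment, and these are in person at Sessions 1 and 6 by default. BrainHQ performance also continues to week 4 as a secondary outcome, but these are trained tasks and not a standardized test.

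**The size is unknown.** Correct. Every percentage above zero shift rests on assumed shifts and SDs. The lack of separation on the default schedule does not.

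**Matching mode would not make the 4-week change causal.** Also correct. Practice effects, home BrainHQ training and permitted medication changes (Section 15.0) would remain confounded with time in a single arm.

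**Conclusion.** The point holds in limited form. On the default schedule, 4-week MoCA change cannot be separated from a change of test mode. With the permitted remote baselines the confounding is large but not total. Table and text disagree on whether a remote baseline MoCA is allowed, and the analysis neither fixes, records nor models mode.

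The consequence is confined to whether cognition held or fell at 4 weeks; the in-person comparison of Sessions 1 and 6 is untouched. If no baselines are remote and a true mode shift of 0.5 to 1.5 points is assumed, with SDs of change of 2 to 3, a false 4-week change would reach nominal significance in 14% to 98% of trials. With no mode shift the figure is the nominal 5%. The documents do not say where in this range the trial lies, or in which direction a shift would go. For an exploratory follow-up measure in a pilot, this is a worthwhile low-cost improvement and not a serious flaw.

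**What to change.** 1. Reconcile the Session 1 row of the schedule table with the Session 1 text on remote MoCA, and state whether the exception extends to Session 6.
2. Record mode and medium (in person, video, phone) at each MoCA.
3. In Section 12.0, base MoCA inference on same-mode comparisons, which by default means Session 1 versus Session 6.
4. If a 4-week contrast is wanted, give the MoCA in the same mode and medium within participant at Sessions 1, 6 and 9, for example by video alongside the items that already have a remote option. If not, keep mode-mismatched Session 9 scores out of the change model and report them descriptively.

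**Cost.** Steps 1 to 3 need wording changes and a data field at each MoCA. Step 4 is a choice. Under matching, some participants lose in-person MoCA administration and need a short video contact, since they still attend for the NIH Toolbox and MRI. Without matching, the default schedule leaves nearly all 4-week MoCA scores for description only. Under either option, practice, home training and medication changes remain as limitations to state in the report.
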